12.2 LISTINGS

12.3 LISTINGS

Adverse Events

Subject Accountability

1. Randomization List (including, subject ID, randomization number, randomized treatment and treatment administered, and date of treatment)
2. Inclusion and Exclusion Criteria
3. Protocol Deviations
4. Subjects Withdrawing from the Study Prematurely (date and reason)
5. Analysis Populations with Reason for Exclusion (if populations differ)

Demographics and Baseline Characteristics

6. Demographics and Baseline Characteristics
[age, sex, race, ethnicity, weight, height, BMI]
7. Medical History
8. Baseline Medication Use

Efficacy

9. FDA Assessment of 14 Common COVID-19-Related Symptoms
10. Borg Dyspnoea Scale
11. Deaths
12. Blood-Oxygen Saturation (SpO2)
13. Six-Minute Walk Test

14. SF-36 Quality of Life Assessment
15. Fatigue Questionnaire
16. Sleep Disturbance Questionnaire
17. Chest Imaging

Safety

18. Exposure to Study Treatment
19. All Adverse Events [with indication of TEAE]
20. Concomitant Medications
21. Vital Signs Data [with flagging of values outside of normal range]
22. ECG Data

12.4 FIGURES (TBD)

**13 HANDLING OF MISSING OR INCOMPLETE DATES FOR
ADVERSE EVENTS AND CONCOMITANT MEDICATIONS**

13.1 IMPUTATION RULES FOR PARTIAL OR MISSING STOP DATES

If the month and year are present, impute the last day of the month. If only the year is present, impute December 31 of that year. If the stop date is entirely missing, assume the event or medication is ongoing. If a partial or complete stop date is present and the ‘ongoing’ or ‘continuing’ box is checked, then it will be assumed that the AE or concomitant medication stopped and the stop date will be imputed, if partial.

		Stop Date						
		Complete: yyyymmdd		Partial: yyyymm		Partial: yyyy		Missing
Start Date		<1 st Dose	≥1 st Dose	<1 st Dose yyyymm	≥1 st Dose yyyymm	<1 st Dose yyyy	≥1 st Dose yyyy	
Partial: yyyymm	=1 st Dose yyyymm	2	1	2	1	N/A	1	1
	≠ 1 st Dose yyyymm		2		2	2	2	2
Partial: yyyy	=1 st Dose yyyy	3	1	3	1	N/A	1	1
	≠ 1 st Dose yyyy		3		3	3	3	3
Missing		4	1	4	1	4	1	1

1 = Impute the date of first dose

2 = Impute the first of the month

3 = Impute January 1 of the year

4 = Impute January 1 of the stop year

Note: For subjects who were never treated (first dose date is missing), partial start dates will be set to the first day of the partial month.

Note: If the start date imputation leads to a start date that is after the stop date, then do not impute the start date.

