10.3 Safety

10.3.1	Exposure to Study Treatment
10.3.2	Incidence and Severity of Treatment-Emergent (TEAE) Events from Baseline to Day 28
10.3.3	Incidence and Severity of Serious Treatment-Emergent (TEAE) Events from Baseline to Day 28
10.3.4	Overall Summary of Treatment-Emergent Adverse (TEAE) Events
10.3.5	Incidence of TEAEs by System Organ Class and Preferred Term
10.3.6	Incidence of Treatment-Emergent Related AEs by System Organ Class and Preferred Term
10.3.7	Incidence of Treatment-Emergent Serious Adverse Events (SAEs) by System Organ Class and Preferred Term
10.3.8	Incidence of TEAEs by Preferred Term in Descending Order of Frequency

10.3.9	Incidence of Treatment-Emergent Related AEs by Preferred Term in Descending Order of Frequency
10.3.10.1	Summary of Pulse Change from Baseline over Time (bpm)
10.3.10.2	Summary of Body Temperature and Change from Baseline over Time (F)
10.3.10.3	Summary of Systolic BP and Change from Baseline over Time (mmHg)
10.3.10.4	Summary of Diastolic BP and Change from Baseline over Time (mmHg)
10.3.10.5	Summary of Respiration Rate and Change from Baseline over Time
10.3.11.1	Concomitant Medication Use by ATC Level 1
10.3.11.2	Concomitant Medications Preferred Term in Descending Order of Use
10.3.11.3	Medication Started on Study Preferred Term in Descending Order of Use

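### SAP 13.1 can date a medicine already in use before treatment to the first dose, and it sets no upper limit on imputed stop dates (minor)

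*SAP*

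**What the plan says.** The heading of SAP section 13 gives its scope as "ADVERSE EVENTS AND CONCOMITANT MEDICATIONS", and SAP 13.1 then supplies a single grid for both. The heading of 13.1 names only stop dates, but the grid also imputes start dates.

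- **Start dates.** Code 1 is "1 = Impute the date of first dose". When the start is entirely missing, the only other code in the row is "4 = Impute January 1 of the stop year", used when the stop is before first dose.
- **Stop dates.** A date that lacks only its day is moved to the end of the recorded month. For a date with less detail the rule is "If only the year is present, impute December 31 of that year". A medicine or event without any recorded stop is taken to be continuing.
- **Check on the result.** The only one is "If the start date imputation leads to a start date that is after the stop date, then do not impute the start date".

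Two planned outputs use these dates. The table list in SAP 12.1 includes Table 10.3.11.3, "Medication Started on Study Preferred Term in Descending Order of Use". SAP 8.3 counts medication use before the study, during it and at the final visit, and compares use between the arms by a chi-square or Fisher's exact test.

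The trial also records prior use directly. Protocol 5.2.2 has concomitant medications recorded at the baseline assessment before treatment, Protocol 5.3 collects prior medications, and Listing 8 in SAP 12.3 shows baseline medication use.

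**The concern.** Moving an uncertain start to the first dose is cautious for an adverse event, because the event then counts as treatment-emergent. The same move on a medicine turns possible prior use into apparent new use. Long-term medicines are plausibly those whose start date a participant cannot give, and they are usually ongoing, which is the combination that code 1 catches. The record may already show that the medicine was in use before the first nebulisation, yet nothing in the grid consults that information.

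The table of newly started medicines could therefore mix new treatment with old, and the prior-use count could be too low. Separately, a stop date imputed to the end of a month or year can lie beyond the period in which the participant was observed.

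**Working it through.** The plan gives no figure on this point, so there is none to reproduce. The check is to apply the written rules to test records.

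**1. Coverage of code 1.** The missing-start row of the SAP 13.1 grid, read across its seven stop-date columns, is 4, 1, 4, 1, 4, 1, 1. Code 1 fills 4 of 7 cells: the three columns with a stop on or after first dose, and the missing-stop column.

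**2. Test records.** Assumed first dose (Day 1): 12 October 2021. Day 60 = Day 1 + 59 days = 10 December 2021.

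| Recorded start | Recorded stop | Code | Imputed start |
|---|---|---|---|
| missing | missing (ongoing) | 1 | 12 Oct 2021 |
| missing | 20 Nov 2021 | 1 | 12 Oct 2021 |
| missing | Oct 2021 | 1 | 12 Oct 2021 |
| missing | 2021 | 1 | 12 Oct 2021 |
| 2021 | missing | 1 | 12 Oct 2021 |
| Oct 2021 | missing | 1 | 12 Oct 2021 |
| missing | 15 Sep 2021 | 4 | 1 Jan 2021 |
| Sep 2021 | missing | 2 | 1 Sep 2021 |
| 2015 | missing | 3 | 1 Jan 2015 |

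The first six records get a start on the day of first dose whatever the baseline medication record shows. The last three are correctly placed before first dose. The problem is thus confined to starts that are missing, or that match the month or year of first dose, with a stop that is missing or on or after first dose.

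**3. Effect on the outputs.** A medicine in use before and after first dose counts as used during the study whether its start is imputed to first dose or to years earlier, so code 1 does not change that count. What can change is prior use (one record fewer) and, if the term means a start on or after first dose, Table 10.3.11.3 (one record more).

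**4. Stop dates.** With the same assumed first dose, a stop recorded only as December 2021, or only as 2021, becomes 31 December 2021, which is 31 − 10 = 21 days after Day 60. To show the range, the first dose was moved over all 365 days of 2021 (also an assumption):

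| Known part of the stop date | Imputed after Day 60 | After Day 63 (end of visit window) | Mean days late | Maximum |
|---|---|---|---|---|
| Month, equal to the month of Day 60 | 97% | 87% | 15 | 30 |
| Year only, equal to the year of Day 60 | 99.7% | 99% | 182 | 364 |

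These percentages apply only to records with such a partial stop date. They do not say how many records there will be, and the documents give no basis for estimating that.

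**The case against.** The strongest reply is that little depends on these dates. Four parts of it stand.

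- **The between-arm test.** A reader might infer that SAP 8.3 tests newly started medication between the arms, so that misdated records could create a false difference. SAP 8.3 tests concomitant use in general, and Table 10.3.11.3 has no planned test. A split of 5 of 15 against 0 of 15 would give a two-sided Fisher p = 2 × 3003/142506 = 0.042, but 4 against 0 gives 2 × 1365/27405 = 0.10. Both splits are chosen for illustration. With randomised, blinded arms there is no reason to expect misdating to fall on one side.
- **The classification.** A reader might infer that every ongoing medicine without a start date will be reported as started on study. The SAP does not define that term, and the baseline record could equally be used to classify medicines. The miscount follows on the natural reading, not from an explicit statement.
- **The number of records.** Protocol 7.3 asks for start and stop dates for all concomitant medications, and these and adverse events are reviewed repeatedly to Day 60. Year-only stop dates within follow-up should be rare.
- **Adverse-event durations.** No duration table is planned, and a late stop date does not change the incidence of treatment-emergent events.

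It would also be wrong to cap every imputed stop date at study exit. Protocol 8.3 follows events continuing at exit for up to 30 days, so a true adverse-event stop can lie after exit.

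The reply does not remove the core point. The written rule assigns a first-dose start even where prior use is documented, and no other sentence in the SAP prevents it.

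**Conclusion.** The point holds as a minor one. Code 1 can give a medicine recorded as prior, or in use at the pre-dose Day 1 review, a start on the day of first dose. Its appearance in Table 10.3.11.3 and its loss from the prior-use count rest on the assumption that started on study means a start on or after first dose. The absence of an upper limit on partial stop dates is certain from the text; its practical effect is that a medicine stopped before the last visit may look in use at that visit.

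The effect is confined to descriptive medication summaries and, for prior or final-visit use, to whatever comparison SAP 8.3 makes of them. The primary endpoint, the efficacy analyses and the incidence of treatment-emergent events do not change, and no bias towards either arm is expected. How many records are affected cannot be derived from the documents.

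**What to change.** In SAP 13.1:

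1. Restrict code 1 to adverse events.
2. Class a medicine with a missing or partial start as prior and ongoing if it was reported as prior, or as in use at the pre-dose baseline review.
3. Define started on study as first reported after the pre-dose baseline review, or having a known start on or after first dose. Use this definition for Table 10.3.11.3.
4. Cap imputed medication stop dates at the earlier of death and study exit. Cap imputed adverse-event stop dates at the earlier of death and the last follow-up contact, in line with Protocol 8.3. In neither case should the cap move a date to before the recorded month or year.

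The cost is a few sentences and a small programming change, best made before unblinding. No new data are needed, because prior medications and the baseline medication review are already collected.

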14 SCHEDULE OF EVENTS

	Screen	Treatment					Post-Treatment Follow-Up		
		1 ²	2	3 ²	4	5 ²	7	28	60
Study Day	-3 to 1								
Visit Window (± days)	--	--	--	--	--	--	3	3	3
COVID-19 tests	X								
Informed consent	X								
Medical history and pre-existing conditions	X								
Electrocardiogram (ECG)	X								
Pregnancy test	X								
Inclusion/exclusion criteria	X	X							
Demographics	X								
Randomization		X							
Treatment ^{1,2}		X	X	X	X	X			
Health check		X		X		X			
Blood oxygen saturation		X					X	X	X
Assessment of 14 Common COVID-19-Related symptoms questionnaire		X					X	X	X
Borg Dyspnoea Scale (mBDS)		X					X	X	X
Walk test		X					X	X	X
Chest x-ray imaging		X ³							X
Concomitant medications ²		X	X	X	X	X	X	X	X
Quality of Life Assessment (SF-36)		X					X	X	X
PROMIS Fatigue questionnaire		X					X	X	X
PROMIS Sleep Disturbance questionnaire		X					X	X	X
Adverse events ²		X	X	X	X	X	X	X	X

¹ Day 1, baseline assessments (health check, blood oxygen saturation, assessment of symptoms/questionnaires, mBDS, walk test, and chest x-ray) should occur before the first dose of treatment. These tests and the first dose of treatment will occur at the clinic. Treatment for the remainder of Day 1 and Days 2, 3, 4, 5 will occur at home.

² Day 1 post-first dose, Day 3 and Day 5 health check, concomitant medications and adverse event collection will occur via telephone visit.

³ Baseline chest x-ray may be performed after Screening, up to 3 days prior to Day 1.

15 APPENDIX

15.1 ASSESSMENT OF 14 COMMON COVID-19-RELATED SYMPTOMS QUESTIONNAIRE

Example items	Example response options and scoring*

For items 1–10, sample item wording could be: “What was the severity of your [insert symptom] at its worst over the last 24 hours?”
	
1. Stuffy or runny nose	
2. Sore throat	
3. Shortness of breath (difficulty breathing)	
4. Cough	None = 0
5. Low energy or tiredness	Mild = 1
6. Muscle or body aches	Moderate = 2
7. Headache	Severe = 3
8. Chills or shivering	
9. Feeling hot or feverish	
10. Nausea (feeling like you wanted to throw up)	
11. How many times did you vomit (throw up) in the last 24 hours?**	I did not vomit at all = 0 1–2 times = 1 3–4 times = 2 5 or more times = 3

continued

Table 1, continued

12. How many times did you have diarrhea (loose or watery stools) in the last 24 hours ??	I did not have diarrhea at all = 0 1–2 times = 1 3–4 times = 2 5 or more times = 3
13. Rate your sense of smell in the last 24 hours	My sense of smell is THE SAME AS usual = 0 My sense of smell is LESS THAN usual = 1 I have NO sense of smell = 2
14. Rate your sense of taste in the last 24 hours	My sense of taste is THE SAME AS usual = 0 My sense of taste is LESS THAN usual = 1 I have NO sense of taste = 2

* Note: Score values are included in the table for ease of reference. FDA cautions against including the score values within the response options presented to trial subjects to avoid confusing subjects.

** The response options shown for items 11 and 12 are intended only for use with a 24-hour recall period.

15.2 BORG DYSPNOEA SCALE

Borg Dyspnoea Scale will be conducted at baseline, Day 7, Day 28, and Day 60. This scale asks you to rate the difficulty of your breathing it starts at number 0 where you are breathing is causing you no difficulty at all and progresses through to number 10 where your breathing difficulty is maximal.

15.3 SIX-MINUTE WALK TEST

The walk test is conducted as follows:

- Flat, straight corridor 30 m (100 feet) in length
- Turnaround points marked with a cone
- Patient should wear comfortable clothes and shoes
- Patient rests in chair for at least 10 minutes prior to test (ie, no warm-up period)
- Heart rate and pulse oxygen saturation (SpO2) should be monitored throughout the test
- If the patient is using supplemental oxygen, record the flow rate and type of device
- Have patient stand and rate baseline dyspnea and overall fatigue using Borg scale*[1]
- Set lap counter to zero and timer to six minutes

- Instruct the patient: Remember that the object is to walk AS FAR AS POSSIBLE for 6 minutes, but don't run or jog. Pivot briskly around the cone.
 - Standardized encouragement statements should be provided at one-minute intervals, such as "You are doing well. You have _ minutes to go" and "Keep up the good work. You have _ minutes to go."
 - At the end of the test, mark the spot where the patient stopped on the floor
 - If using a pulse oximeter, measure the pulse rate and SpO2 and record
 - After the test record the Borg*[1] dyspnea and fatigue levels
 - Ask, "What, if anything, kept you from walking farther?"
 - Calculate the distance walked and record
1. Borg GA. Psychophysical bases of perceived exertion. *Med Sci Sports Exerc* 1982; 14:377.
 2. American Thoracic Society. ATS statement: Guidelines for the six-minute walk test. *Am J Respir Crit Care Med* 2002; 166:111.
